### 3.2.3 SWOT analysis

STRENGTHS
 
 
- Applicable to anastomosis located over 7 cm from the anal verge
 
- High risk of stoma-related complications
 
- Psychological impact of a stoma
 
- Possibility to improve patient's outcome and reduce hospital costs
 
- Low cost of the new treatment
 
	
WEAKNESS
 
 
- High number of patients to be recruited
 
- Variability of the techniques
 

OPPORTUNITIES
 
 
- Applicable to a relevant proportion of patients affected by Rectal cancer which is one of the most frequent human cancer.
 
- Reduce number of stomas, stoma related complications and new operations for stoma closure
 
- Reduce hospital costs
 
- Improvement of the patients QoL
 
	
THREATS
 
 
- Risk of sepsis for anastomotic leakage (?)
 

### 3.3 Randomization

Written informed consent will be obtained prior to surgery by the operating surgeon. Computer-generated randomization will be used to create an allocation sequence to assign patients to the different study arms. Randomization will be computer generated and centrally controlled by an operator not involved in the study. Patients will be randomized only after completion of neoadjuvant chemo radiation (when indicated) and before surgery.

#### **3.4. Subject Recruitment and Screening**

Each patient referred for elective resection found eligible per stated inclusion and exclusion criteria will be approached by the operating surgeon. The patient will be informed about the study as per IRB protocol and consent. Patients will be given information about the risks, discomforts, and potential benefits of both treatments. The randomization protocol will be explained to the patient before consent is obtained.

#### **3.5 Participating Institution and Surgeons**

This multicenter trial is opened to the contribution of surgeons across Europe in order to achieve the required number of patient recruitment in the shortest period.

- All surgeons must have prior experience in performing colorectal cancer surgery either in open or laparoscopic route.
- All participating institutions must have IRB (Institutional Review Board)/Ethics Committee approval in order to enroll patients in the trial.
- As part of educational interventions, all participating surgeons will preview a video of the surgical technique of the application of nebulised cyanoacrylate glue.
- Recruitment of Centers will be by direct invitation or spontaneous proposal of Colorectal Units interested in the study.

#### **3.6 Definition of Outcome Measures**

Please use the following definitions:

- estimated blood loss (ml) recorded by the anaesthesiologist (not by the surgeon)
- duration of hospital stay (defined as from beginning of surgery to time of discharge, measured in days)
- Anastomotic leak will be confirmed by one or more that the following conditions
  - fecal discharge from the pelvic drainage at any time after surgery
  - rectovaginal fistula defined as fecal or mucus discharge from the vagina
  - pelvic sepsis as defined by the collection of pus/ fecal material in the pelvis documented by CTscan
  - Two sides X- Ray proctography performed by introducing 100 ml of hydro soluble liquid contrast medium (Gastrographin NOT barium sulphate) through the anus over the anastomotic line, by a Foley catheter (with an empty balloon) with the patient in standing position. The Foley catheter must be withdrawn after injection of the contrast medium and before the X Rays in order to prevent false-negative results.

**Classification of the anastomotic leak:** Grade A anastomotic leakage results in no change in patients' management, whereas grade B leakage requires active therapeutic intervention but is manageable without re-laparotomy. Grade C anastomotic leakage requires re-laparotomy (according to Rahbari NN, et al. Surgery 2010)

### **3.6.1 Definition of Adverse Events**

- Primary ileus will be defined as bowel dysfunction occurring after surgery for a duration greater than 10 days and that requires intervention including nil per os (NPO) status, naso-gastric tube, medication, or surgery.

- Secondary ileus will be defined as bowel dysfunction that occurs after the patient has resumed oral nutrition after surgery, and that requires intervention including NPO status, naso-gastric tube, medication, or surgery.
- Urinary tract infection (UTI)
  - Symptomatic urinary tract infection must meet at least 1 of the following criteria:
    - fever (>38°C), urgency, frequency, dysuria, or suprapubic tenderness *and* patient has a positive urine culture, that is,  $\geq 10^5$  microorganisms per cc of urine with no more than 2 species of microorganisms.
- Urinary retention will be defined as the condition of urinary dysfunction that occurs following surgery and requires intervention, including placement of urinary catheter.
- Pyrexia will be defined as any documented patient temperatures >38.0 C that require any treatment intervention such as antipyretics or that result in an increase in hospital stay.
- Wound dehiscence is defined as a delayed opening of the abdominal scar, without evidence of infection.
- Rectovaginal fistula defined as fecal or mucus discharge from the vagina
- Surgical site infection purulent discharge from the wound with positive culture
- Pulmonary infection documented by Chest X Ray

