### **1. Background**

Colorectal cancer (CRC) is the second most common cause of cancer-related death in male and the third in females in Western Countries accounting for more than 500,000 deaths in 2013 worldwide(1).

One of the most worrying postoperative complication in colorectal surgery is the anastomotic leak which can occur in about 10-15% of the cases(2).

This complication severely impact clinical outcomes with increased risk of death or permanent stoma, higher risk of local recurrence) and relevant increase in hospital costs (length of hospital stay, admission to intensive care, re-interventions)(3).

The problem of anastomotic leak is particularly relevant in rectal surgery. The more distal the anastomosis, the higher the likelihood of failure, with resection of a distal rectal cancer having almost a five-fold increased risk of anastomotic leak compared with resection for colon cancer(4).

In fact, anastomotic Leakage (AL) is the most severe complication after Low anterior resection of rectum for cancer, occurring between 3 and 24 % of patients(5).

Many risk factors have been recognized in the onset of this complication(6), including gender (male patient have a higher anastomotic leak rate)(7), malnutrition, obesity an diabet, ASA score, tobacco use, cardiovascular disease, immunosoppression, use of NSAID(8), preoperative pelvis radiation.

Other intraoperative risk factors considered are the splenic flexure mobilization with proximal ligation of the IMA(9), positive intraoperative Air-Leak Test(10) and the perfusion of the anastomosis (11).

Temporary fecal diversion has also been suggested (although a diverting stoma mitigates the clinical consequences of an anastomotic leak but does not prevent it(12).

Other intraoperative technical factors include the use of single or double stapled anastomotic techniques, with or without transanal reinforcing sutures(13).

Therefore, preventing the anastomotic leak can bring benefits to the patient and the health system.

All the risk factors described above rapresent the rationale that justifies the use of intraoperative procedures to prevent the anastomotic leak, such as additional manual stiches to the mechanical suture and / or patches of collagen (proper reinforcement or buttressing) or of sealants.

Several attempts have been proposed to reduce the risk of AL in low rectal cancer surgery including

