### 3.2.2 Secondary

**SAFETY:** Demonstration that the new treatment will not add related morbidity

**EFFICACY:** Demonstrate that anastomotic reinforcement with cyanoacrylate decrease the rate of anastomotic leakage

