### **3.6.2 Classification of the postoperative complications**

- The Clavien Dindo Classification for postoperative complications will be adopted (see attached form 9.2)
- The Comprehensive Complication Index

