### **5.2 Statistical Methods:**

All statistical analysis will be done in an intention-to-treat fashion. No interim analyses are planned. For all statistical tests, a P value of .05 will be considered significant. A Student t-test will provide an unadjusted estimate of the difference between treatment arms. Analysis of covariance, a more robust method that allows control for key differences in baseline characteristics, will be used to provide adjusted comparisons.

Like the primary outcome, continuous secondary outcomes (such as safety and efficacy) will be modeled by t-tests and analysis of co-variance.

Any relationship of the anastomotic leakage with other possible adverse factors will be evaluated by univariate and multivariate regression analysis

When the complete case analysis will exclude more than 5% of patients due to missing data, exploratory analyses to investigate the effect of missing data will be performed. In order to explore the mechanism of the missing data and the validity of a complete case analysis for each end point, patient characteristics will be compared between those with and without missing data and multilevel logistic regression models will be used to identify any associations between prognostic variables and to inform if data are missing at random.

Multilevel logistic regression will be used to estimate the odds ratios (ORs) for conversion to laparotomy, intraoperative complications, and postoperative complications between treatment groups.

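### No measure is named for the safety objective, and the morbidity measures that are named do not exclude anastomotic leak, so a benefit on leak can partly hide a rise in other complications

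*Combined protocol and SAP*

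**What the plan says.** The secondary safety objective in section 3.2.2 is "Demonstration that the new treatment will not add related morbidity". No event list, scale, margin or attribution rule is attached to it.

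Morbidity is described in three other places:

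- Section 3.6.1 lists adverse events, among them "Rectovaginal fistula defined as fecal or mucus discharge from the vagina".
- Section 3.6.2 states "The Clavien Dindo Classification for postoperative complications will be adopted" and adds "The Comprehensive Complication Index". Neither is restricted to events other than leak.
- Section 5.2 says that "continuous secondary outcomes (such as safety and efficacy) will be modeled by t-tests and analysis of co-variance", without naming the variable. It also plans odds ratios from multilevel logistic regression, one of them for postoperative complications taken as a group.

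The primary event is defined in section 3.6: "Anastomotic leak will be confirmed by one or more that the following conditions". One of those conditions is "rectovaginal fistula defined as fecal or mucus discharge from the vagina"; the others are faecal drain discharge, a pelvic collection on CT, and contrast proctography. Section 3.6 also grades leak A to C by the intervention it needs. The Background counts leak among postoperative complications: "One of the most worrying postoperative complication in colorectal surgery is the anastomotic leak".

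Nothing in the available text plans a morbidity comparison with leak events removed.

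**The concern.** Efficacy and safety are meant to answer different questions: does the glue prevent leak, and does it cause anything else? If the measure used for the second question contains the events of the first, the answers are linked. Under the trial's own hypothesis, fewer leaks lower the glue arm's complication total and offset any new morbidity. The trial could then report no added morbidity although non-leak complications had risen, and a reader could not tell this from the pooled result.

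**Working it through.** The plan states no morbidity rate, so there is no figure of its own to reproduce here. The leak rates and arm size come from section 6.1 and are used only as inputs; whether 67 per arm is justified for the primary endpoint is a separate matter.

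**Inputs**

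- Leak (6.1): L = 16% control, 10% glue.
- Arm size (6.1): 67.
- Other (non-leak) complications in controls (assumed): M = 15%, 25% or 35%.
- True harm of the glue on other complications (assumed): +6 points. This equals the leak benefit, so near-cancellation under independence is partly a result of that choice.

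**Step 1. Leak and other complications independent**

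Any complication = 1 − (1 − L)(1 − M).

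| Other: control → glue | Any, control | Any, glue | Difference | OR with leak | OR without leak |
|---|---|---|---|---|---|
| 15% → 21% | 1 − 0.84×0.85 = 28.6% | 1 − 0.90×0.79 = 28.9% | 0.3 | 1.01 | 1.51 |
| 25% → 31% | 1 − 0.84×0.75 = 37.0% | 1 − 0.90×0.69 = 37.9% | 0.9 | 1.04 | 1.35 |
| 35% → 41% | 1 − 0.84×0.65 = 45.4% | 1 − 0.90×0.59 = 46.9% | 1.5 | 1.06 | 1.29 |

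**Step 2. Maximum overlap**

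If the two kinds of event coincide in the same patients as far as possible, any complication = max(L, M).

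- 15% → 21%: 16% v 21%, difference 5 points.
- 25% → 31%: 25% v 31%, difference 6 points.
- 35% → 41%: 35% v 41%, difference 6 points.

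Most or all of the harm then remains visible.

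**Step 3. The fistula line alone**

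Suppose fistula makes up 2% to 20% of leaks (assumed) and other complications run at 20% in controls (assumed). At the top of that range, fistula occurs in 0.20×16% = 3.2% v 0.20×10% = 2.0%. The control total is 1 − 0.968×0.80 = 22.56%. The glue arm reaches the same total when its other complications are 1 − 0.7744/0.98 = 20.98%, so about 1.0 point is hidden. At a 2% share the same sum gives about 0.1 point.

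**Step 4. Power with leak removed**

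For two proportions, power = Φ[(d − 1.96·se₀)/se₁], two-sided 5%, 67 per arm. For 20% v 26%:

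- se₀ = √(0.23×0.77×2/67) = 0.0727
- se₁ = √[(0.20×0.80 + 0.26×0.74)/67] = 0.0725
- power = Φ[(0.06 − 0.1425)/0.0725] = Φ(−1.14) = 12.8%

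The same formula gives 17.6% for 10% v 16% and 11.0% for 30% v 36%.

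**The case against.** The strongest reply is that the documents do not say leak is part of the safety measure. Section 3.2.2 links no measure to the objective, and the word for related morbidity can be read as morbidity attributable to the glue. Leak has its own definition and A-to-C grading, apart from the adverse event list, and apart from fistula no item on that list is a leak criterion. Item-by-item adverse event tables would be largely unaffected, except for the fistula line and events that follow from a leak. The Clavien-Dindo form is not in the available text, so it cannot be checked whether it records leak separately.

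This stands as a limit. A reader might infer that the plan has adopted a safety endpoint containing leak, or that the repeated fistula definition is itself the source of the masking. The first is not stated, and step 3 contradicts the second. What remains is that the only comparison of complications as a group is a pooled odds ratio, no text excludes leak from it or from the two scales, and the Background counts leak as a postoperative complication.

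A second reply is that total morbidity is a legitimate measure of net harm. Leak and pelvic sepsis could themselves be caused by a locally applied glue, and the threats listed in section 3.2.3 include sepsis from leakage. That is right. It argues against letting a leak-free version decide alone, but not against showing it. Likewise, leak counting against the glue on both efficacy and safety if the glue raises leak is not an error.

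**Conclusion.** The point holds as a gap with a foreseeable direction of bias. The safety objective has no named measure, and every aggregate morbidity measure in the plan can absorb the efficacy effect. At the planned leak benefit, a 6-point rise in other complications would appear in a pooled binary comparison as 0.3 to 1.5 points under independence and as 5 to 6 points under maximum overlap, for assumed control rates of 15% to 35%. Where the truth lies depends on how often leak and other complications occur in the same patients, which the documents do not say. Nothing has been computed for the Clavien-Dindo or Comprehensive Complication Index comparisons.

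A reader might infer that the trial would conceal nearly all of such a harm. That follows only under independence and with a harm set equal to the leak benefit, so the documents do not support it as a general statement. The primary analysis is not affected.

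Separating out leak would also not make the trial able to rule out harm. Power for a 6-point rise is about 11% to 18% with 67 per arm, so a non-significant result in either version is weak evidence.

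**What to change.** In sections 3.2.2 and 5.2:

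1. Name the safety measures: the postoperative complication odds ratio, Clavien-Dindo grade and the Comprehensive Complication Index.
2. Report each one twice, in total and excluding events that meet the leak definition in 3.6, with estimates and 95% confidence intervals.
3. Require the safety statement to consider both versions, with neither alone decisive.
4. State that a non-significant difference in either version will not be reported as showing no added morbidity.
5. Fix in advance a simple rule for complications secondary to a leak (for example, an ileus or fever that follows one), applied identically in both arms. The documents describe no blinding, so the rule should leave as little as possible to judgement.

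The cost is a change of wording, one extra tabulation and model run from data already collected, and an attribution item on the form. No more patients or visits are needed. The main downside is that attributing secondary events will sometimes be uncertain; the total version, shown alongside, does not depend on it.

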### **3.6.2 Classification of the postoperative complications**

- The Clavien Dindo Classification for postoperative complications will be adopted (see attached form 9.2)
- The Comprehensive Complication Index

## **3.7 ELIGIBILITY CRITERIA**

### **3.7.1 Inclusion Criteria**

- Resectable, histologically proven primary adenocarcinoma of the High-medium rectum without internal and/or external sphincter muscle involvement.
- Distal margin of the tumor at least 8 cm from the anal verge
- Staged as follows prior to neoadjuvant chemoradiation:
  - Stage T2 - T4 at MRI
- Patient classified T3-T4 will undergo neoadjuvant chemoradiation if the cancer is located in the extraperitoneal rectum

### **3.7.2 Exclusion Criteria**

- Squamous cell carcinoma
- Adenocarcinoma Stage T1,
- T4 with one of the following:
  - with pelvic side wall involvement
  - requiring sacrectomy
  - requiring prostatectomy (partial or total)
- Unresectable primary rectal cancer or Inability to complete R0 resection.
- Rectal cancer under 8 cm from the anal verge requiring colo-anal or ultra low rectal anastomosis
- Recurrent rectal cancer
- Previous pelvic malignancy
- Inability to sign the informed consent

### **3.8 Withdrawal Criteria**

Study participants will be informed of their ability to withdraw from the study or refuse initial enrollment at any time. Patients may withdraw without explanation.

## **4 STUDY INTERVENTION**

### **4.1 Preoperative work-up**

Patients will be seen for preoperative evaluation within 2 weeks prior to surgery. All tests and evaluations should be completed prior to surgery.

- All subjects will receive bowel prep per institutional routine.
- The entire colon should be investigated by a colonoscopy.
- Proctoscopy should be performed to assess the localization of the tumor and the distance from the anal verge.
- Histological confirmation of the tumor prior to surgery is mandatory.

Preoperative Tumor and nodal staging should be done by MRI and /or endorectal ultrasonography

#### **4.1.1 Timing of surgery after Neoadjuvant Chemoradiation**

Surgery must occur within 8-12 weeks (56-84 days) after completion of neoadjuvant therapy when indicated

### **4.2 Operative protocol**

- Anesthetic care will include general endotracheal anesthesia with gastric and bladder catheterization.
- Epidural catheter may be used for post-operative pain control.

#### **4.2.1 Technique**

Patient preparation to rectal surgery will follow the general Rules for Good Clinical Practice. Mechanical bowel preparation using oral PEG solution will be used according to surgeon preference, antibiotic and antithrombotic prophylaxis will start immediately before surgery.

Patient Position: Lithotomy position for abdominal and perineal procedures.

Abdominal procedure (open or laparoscopic) will be carried out according the oncological guidelines included total mesorectal excision with adequate lymph-node retrieval, at least 1 cm of distal clearance. A termino-terminal, latero-terminal, colorectal knight-Griffen anastomosis.

Both groups of patients will have a pneumo-hydraulic test after the completion of the anastomosis.

#### **4.2.1.1 NO CYANOACRYLATE GROUP**

Patients selected in the no cyanoacrylate glue arm will not have anastomotic reinforcements

#### **4.2.1.2 CYANOACRYLATE GROUP**

Patients selected in this group will receive the anastomotic reinforcement with nebulized cyanoacrylic glue using the special short catheter device for open surgery or the laparoscopic catheter.

### **4.3 Post-Operative Management**

Postoperative care will be according to current standards as directed by the operative surgeon.

- Pain control will initially be provided using parenteral (intramuscular, intravenous or epidural) administration of narcotics or analgesics.
- Oral analgesics will be offered ad lib when the patient has resumed oral intake.
- The initiation of oral intake and dietary advances will be made according to individual patient tolerance.
- Intravenous fluids will consist of maintenance crystalloid solution in addition to blood products as needed until the patient is able to sustain oral intake.
- Hospital discharge will occur only after the patient has shown diet tolerance, return of bowel function and ability to resume self-care with minimal assistance.

Subjects will return to the PIs ambulatory clinic for a post-op 30-day follow-up visit in order to collect the post-operative data and the post-operative proctography to document the integrity of the anastomosis. If

the subject does not come for the follow-up, the research nurse will contact him/her by all means available (phone, email, mail) to ascertain whether the patient had any complications and/or adverse events that were treated at another institution. If the research nurse is unsuccessful in contacting the patient, this subject will be considered 'lost to follow-up'.

**5. DATA MANAGEMENT:** Data will be collected by a combination of the study investigators, nurse research coordinators, and trained residents and fellows. Baseline characteristics and clinical data, procedural data, and postprocedure outcomes will prospectively entered into a secure database available to each participating center.

## **6 STATISTICAL ANALYSIS**

### **6.1 Sample Size Determination:**

The mean percentage of anastomotic leak after rectal cancer is 16% and its reduction to 10% is considered to be clinically significant. Therefore, the interval of confidence calculated is 12. A sample size calculation shows that 67 subjects per arm will suffice for accepting of the hypothesis with a power of 0.8 and a type I error probability of 0.05, with a Confidence level of 95% (sample size calculated by R Studio Version 1.1.419 – © 2009-2018 RStudio, Inc.). Accounting for a predicted 5% estimated loss to follow-up, a total of 138 (134+4) patients will be included in the study.

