### **3.2 Endpoints**

#### **3.2.1 Primary**

The aim of the trial is to observe a significantly lower number of anastomotic leak of a colorectal anastomosis in the group of patients treated with cyanoacrylate glue

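### Section 6.1 claims 80% power to detect a fall in leak rate from 16% to 10%, but 67 patients per arm give about 18% (two-sided) or 27% (one-sided).

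*Combined protocol and SAP*

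**What the plan says.** Section 6.1 (Sample Size Determination) sets the effect: "The mean percentage of anastomotic leak after rectal cancer is 16% and its reduction to 10% is considered to be clinically significant". It goes on: "Therefore, the interval of confidence calculated is 12", with no unit and no explanation. It then concludes: "A sample size calculation shows that 67 subjects per arm will suffice for accepting of the hypothesis with a power of 0.8", with a type I error of 0.05 and 95% confidence. It names R Studio as the software but gives no formula, test or sidedness. On losses it says: "Accounting for a predicted 5% estimated loss to follow-up, a total of 138 (134+4) patients will be included in the study".

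Section 5.2 (Statistical Methods) gives the unadjusted analysis: "A Student t-test will provide an unadjusted estimate of the difference between treatment arms". It adds "For all statistical tests, a P value of .05 will be considered significant", again without sidedness, and plans no interim analysis. Section 3.1 calls the trial a superiority trial. Section 3.2.1 gives its purpose: "The aim of the trial is to observe a significantly lower number of anastomotic leak" in the glue group. No section gives a second effect size for the calculation.

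**The concern.** A 6-point difference between two proportions near 13% is small compared with the sampling error of two groups of 67. The expected counts are 0.16 × 67 = 10.7 leaks against 0.10 × 67 = 6.7, a gap of four events. A trial of that size would not normally detect such a gap four times in five.

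The primary aim is a statistically significant reduction, so the power figure tells ethics committees and patients how likely the trial is to answer its question. If the figure is badly overstated, a non-significant result is the likely outcome even if the glue works as well as hoped. The stated 0.8 would then invite readers to take that result as evidence of no benefit.

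**Working it through.** **Inputs.** From section 6.1: p₁ = 0.16, p₂ = 0.10, difference 0.06, type I error 0.05, power 0.8, n = 67 per arm. Sidedness is not stated, so both are run (z = 1.960 two-sided, 1.645 one-sided; 0.842 for 80% power). Mean rate p̄ = 0.13.

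**1. Trying to reproduce 67.** The usual two-proportion formula is

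n = [z_α √(2p̄(1−p̄)) + z_β √(p₁(1−p₁) + p₂(1−p₂))]² / (p₁−p₂)²

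with √(2 × 0.13 × 0.87) = 0.4756 and √(0.1344 + 0.0900) = 0.4737.

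- Two-sided: (1.960 × 0.4756 + 0.842 × 0.4737)² / 0.0036 = 1.771 / 0.0036, giving **492 per arm** (525 with continuity correction).
- One-sided: (1.645 × 0.4756 + 0.842 × 0.4737)² / 0.0036 = 1.395 / 0.0036, giving **388 per arm** (421 with continuity correction).

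Unpooled-variance and arcsine versions give 490 and 488 two-sided, and 386 and 384 one-sided. Comparing one group with a fixed rate gives 179 to 262. No version gives 67.

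**2. Power at 67 per arm.** Power = Φ[(0.06√67 − z_α × 0.4756) / 0.4737], with 0.06√67 = 0.4911.

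- Two-sided: Φ(−0.931) = 0.176.
- One-sided: Φ(−0.615) = 0.269.

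Exact enumeration over all possible tables, with the normal approximation for comparison:

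| Test | Two-sided | One-sided |
|---|---|---|
| Normal approximation | 17.6% | 26.9% |
| Pearson chi-square, exact power | 17.3% | 27.4% |
| Student t on leak yes/no (section 5.2) | 17.3% | 27.4% |
| Fisher's exact test | 12.0% | 19.7% |

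**3. Other readings.**

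- If 67 were a slip for 134 per arm, power would be 30.8% or 42.7%.
- If the 12 meant a 12-point fall (16% to 4%), power at 67 per arm would be 64–68% two-sided or 75–79% one-sided by the normal approximation and exact Pearson. Fisher gives 55% or 70%. The numbers needed for 80% power would be 97 or 77 per arm.

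**4. What 67 per arm can detect.** With a 16% control rate, 80% power is reached only if the glue rate is about 2.2–2.8% (two-sided) or 3.4–3.8% (one-sided). In each range the lower figure is the normal approximation and the higher is exact Pearson.

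**5. What results would look like.** Uncorrected Pearson, two-sided, with 11/67 control leaks:

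- 7/67 with glue, almost exactly the target: P = 0.31 (Fisher 0.45)
- 4/67: P = 0.055
- 3/67: P = 0.024

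The 95% interval around an observed 6-point difference is 0.06 ± 1.96√(0.1344/67 + 0.0900/67) = 0.06 ± 0.113, or about −5 to +17 points.

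**6. Possible origin of 67 (inference only).** The precision formula for one proportion with p = 0.5 and a 12-point half-width gives 1.96² × 0.25 / 0.12² = 66.7, which rounds up to 67. This fits the 67, the 12 and the 95% confidence level. It uses no power and neither leak rate. The plan does not mention p = 0.5; its own rates would give 36 (at 16%) or 25 (at 10%).

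**7. Loss to follow-up.** 4/138 = 2.9%. A 5% loss needs 134/0.95 = 141.05, so 142 with equal arms. With 138 enrolled, 138 × 0.95 = 131 remain and power stays near 17%.

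**The case against.** The strongest defence is covariate adjustment, since section 5.2 plans an analysis of covariance. To bring the requirement down to 67, covariates would have to explain about 1 − 67/492 = 86% of the outcome variance two-sided, or 1 − 67/388 = 83% one-sided. Nothing in the documents supports that, and section 6.1 claims no such gain.

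Several smaller points do stand:

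- The origin of 67 is conjecture. It is not evidence of the error, which stands without it.
- Some figures depend on the method. Fisher's test gives lower power and larger P values throughout, so showing only Pearson or the normal approximation would flatter the plan.
- The detectable rates of 2–4% hold only for a 16% control rate. Section 1 cites a wider range of leak rates, so the condition must be stated with them.
- The calculation assumes exactly 67 per arm. The simple randomization in the Randomization section does not guarantee this; imbalance would lower power slightly.
- The loss-to-follow-up slip is trivial beside the power error and would not need urgent correction on its own.
- Correcting the power statement makes the text accurate but does not make the trial adequate for its target. Ethics committees would be asked to accept a trial with about 18% power, so the cost is more than editorial, and the sponsor should make that choice openly.

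**Conclusion.** The concern holds. For 16% versus 10% at a type I error of 0.05, power with 67 per arm is about 18% two-sided or 27% one-sided, against the stated 80%. The chance of missing the target effect is about 82% or 73%, not 20%. The sample size is short by a factor of 492/67 = 7.3 two-sided or 388/67 = 5.8 one-sided, which no choice of test, sidedness or rounding can explain. This rests on the plan's own two rates, a yes/no leak outcome, and equal arms with no loss; relaxing the last two only lowers power. It must be corrected, because it is a false statement about the primary comparison. The 5% loss allowance is also wrong, but of little consequence.

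**What to change.** Amend section 6.1 to:

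1. Name the primary test and its sidedness.
2. Replace 0.8 with the true power for 16% versus 10%: about 18% if two-sided, about 27% if one-sided.
3. State that, with a 16% control rate, 67 per arm reaches 80% power only for a fall to about 2–3% (two-sided) or 3.4–3.8% (one-sided).
4. Explain the 12 or remove it.
5. State 142 patients, or state that 138 with 5% loss leaves about 131 evaluable (minor).
6. As good practice rather than a correction, commit to reporting the risk difference with its 95% confidence interval and to not reading P > 0.05 as evidence of no benefit.

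The superiority aim in sections 3.1 and 3.2.1 can stay. The cost is a wording amendment notified to the ethics committees (section 6.2, Institutional Review Boards), with at most 4 extra patients and a much less favourable power statement.

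If the sponsor instead wants 80% power for 16% versus 10%, the evaluable total is 2 × 492 = 984 two-sided (984/0.95, so 1,036 enrolled) or 2 × 388 = 776 one-sided (776/0.95 = 816.8, so 818 enrolled with equal arms). The amendment should make clear which course was chosen.

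### The 138 enrolled patients are said to allow for 5% loss to follow-up, but 134+4 allows for only about 2.9% (minor, wrong as written)

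*Combined protocol and SAP*

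**What the plan says.** The Sample Size Determination section (6.1) states that "67 subjects per arm will suffice", which makes 134 for two equal arms. It then sets enrolment: "Accounting for a predicted 5% estimated loss to follow-up, a total of 138 (134+4) patients will be included in the study". The base, the loss rate, the increment and the total are therefore all printed, and no other section gives a different total or explains the 4.

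Two other sections bear on what loss means here. Section 4.3 (Post-Operative Management) schedules a 30-day visit at which the post-operative data and the proctography are collected. It counts a patient as lost if that visit is missed and the research nurse cannot make contact. Section 5.2 (Statistical Methods) specifies intention-to-treat analysis and also refers to a complete-case analysis, with exploratory work if more than 5% of patients are excluded. It gives no rule for imputing a missing leak outcome.

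**The concern.** An allowance for loss is meant to leave the required number of patients once the predicted loss has occurred. Here the increment is visibly smaller than the stated percentage: 5% of 134 is 6.7, yet 4 were added. If loss runs exactly as predicted, the trial finishes below the number that the same paragraph says is enough. At stake is the accuracy of a headline design figure that every ethics committee will read. There is also a risk that the same slip is carried over when the sample size is recalculated.

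**Working it through.** **Inputs, all from section 6.1 unless noted**
- Base: 67 per arm, 2 × 67 = 134.
- Predicted loss: d = 5%.
- Stated enrolment: 138, shown as 134 + 4.
- Leak rates: 16% in controls ("The mean percentage of anastomotic leak after rectal cancer is 16" per cent) and 10% as the target ("its reduction to 10% is considered to be clinically significant").
- Power and error rate: "with a power of 0.8 and a type I error probability of 0.05".
- Sidedness is not stated. Section 5.2 says only "For all statistical tests, a P value of .05 will be considered significant". Two-sided is assumed below; the loss arithmetic does not depend on it.

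**Step 1. Try to reproduce 138**
- N/(1 − d) = 134/0.95 = 141.05, which rounds up to 142 for equal arms (67/0.95 = 70.5, or 71 per arm).
- N × (1 + d) = 134 × 1.05 = 140.7, which rounds up to 141.
- Neither gives 138. The increment should be 7 or 8, depending on convention and rounding, not 4.
- Five per cent of one arm is 0.05 × 67 = 3.35, which rounds up to 4. The allowance may have been applied to one arm only, but this is an inference.

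**Step 2. What 138 does cover**
- 4/138 = 2.9% of enrolment (4/134 = 3.0% of the base).
- At 5% loss: 138 × 0.95 = 131.1 patients remain, and 134 − 131.1 = 2.9 is the shortfall.

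**Step 3. Effect on power, 16% v 10%, two-sided 0.05**

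The normal approximation with pooled variance under the null is Φ[(0.06√n − 1.96 × √(2 × 0.13 × 0.87)) / √(0.16 × 0.84 + 0.10 × 0.90)], where n is the number per arm.
- n = 67: (0.4911 − 0.9322)/0.4737 = −0.931, power 17.6%.
- n = 131.1/2 ≈ 65.5: (0.4856 − 0.9322)/0.4737 = −0.943, power 17.3%.
- Difference: about 0.3 percentage points.

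**Step 4. The base figure, for context**
- For 80% power the same formula gives n = [(1.96 × 0.4756 + 0.8416 × 0.4737)/0.06]² ≈ 492 per arm, 984 in all. With a continuity correction it is 525 per arm; one-sided it is 388, or 421 with correction. None is near 67.
- 1.96² × 0.25/0.12² = 66.7, so 67 matches a single-proportion precision formula with p = 0.5 and a half-width of 12 points. This would fit the otherwise unexplained statement "Therefore, the interval of confidence calculated is 12", but again it is an inference.

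**The case against.** The strongest case on the other side is about weight, since the arithmetic itself cannot be defended. The gap is about 3 patients and 0.3 points of power, and no estimate or test would change. The 67 per arm will not survive recalculation from the stated rates, so correcting the total built on it achieves little by itself. All of this stands, and it is why the point is rated minor.

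Intention-to-treat might be thought to remove the problem because every randomized patient is kept. It does so only in part. Section 3.6 (Definition of Outcome Measures) lets a leak be confirmed at any time after surgery by drain discharge, and also by fistula or CT findings. Some patients who are lost later will therefore already have a recorded leak, and subtracting the full 5% is an upper bound on missing outcomes. For the others, freedom from leak at 30 days is unobserved, and section 5.2 gives no imputation rule to bring them back.

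A reader might infer stronger things that the documents do not support:
- *That enrolling 142 would repair the sample size.* It would restore the plan's own 134 after 5% loss, but 134 gives only about 18% power for 16% v 10%. It would also mean four more patients and would make an unsupported total look corrected.
- *That each arm will end with 65 or 66 patients instead of 67.* The Randomization section specifies simple randomization without fixed arm totals. With 138 patients each arm's size has a standard deviation of √138/2 ≈ 5.9, so per-arm counts are expectations only, and chance imbalance is larger than the gap.
- *That the loss allowance is why the trial is underpowered.* Step 3 shows that it contributes almost nothing.

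**Conclusion.** The statement is wrong as written, and the error is minor. The total of 138 allows for about 2.9% loss, not 5%; at 5% loss about 131 patients are expected to remain, roughly 3 below the plan's own 134. The cost in power is about 0.3 points (17.3% v 17.6%).

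The arithmetic takes the plan's 134 as given and treats every lost patient as having no usable outcome. The power figures further assume a two-sided 0.05 test and equal arms. The conclusion about the allowance does not depend on where the 4 came from, or on whether 67 per arm is right. It would remain an error if 67 were correct, but it is far smaller than the problem with 67 itself.

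**What to change.** Restate the last sentence of section 6.1, for example: *Enrolment of 138 allows for a loss of about 2.9%; at the predicted 5% loss, about 131 patients are expected to remain, against the 134 calculated.* This costs one sentence and no patients. The only downside is a slightly less favourable stated figure.

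When the base sample size or its stated power is corrected, apply n/(1 − loss) to the total across both arms. The rule matters more at a larger size: on 984 patients, 984/0.95 = 1035.8, so 1036, an addition of 52. Five per cent of one arm would add only 0.05 × 492 = 24.6, so 25.

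Do not change the total to 142 as a stand-alone correction. Any change in enrolment should follow from a reworked base calculation.
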